3 EXPECTED RISKS/BENEFITS

The data accumulated in this study will advance our understanding of the pathophysiology of gastroparesis, and may provide important information on whether olanzapine is helpful in the treatment of idiopathic gastroparesis.

There are potential direct benefits for all gastroparesis subjects in this study. On study entry, physiologic tests of gut function and motility will be performed that may provide new insight into causes of symptoms in patients with IBS. In addition, all subjects will be seen by the PI and/or study team frequently during the study. Adverse events, vital signs, and laboratory parameters will be assessed to monitor overall safety and tolerability of the medication. Survey information will also be obtained using validated questionnaires including GCSI-DD, appetite VAS, and BSFS. The GCSI-DD is a validated questionnaire composed of twelve questions that takes approximately 10 minutes to complete. The appetite VAS is a single item questionnaire that tracks changes in appetite over time. This will take approximately 1 minute to complete. The BSFS is a questionnaire that allows researchers and subjects track changes in bowel form and frequency. This will take approximately 1 minute to complete. This frequent and comprehensive assessment provided as part of participating in this study may allow for closer monitoring of disease course.

There are potential risks for subjects, including:

1. Olanzapine Risks:

Weight gain: Weight gain is a known risk when patients with schizophrenia or other psychiatric illnesses are taking olanzapine. This may also predispose the patient to develop underlying obesity, hyperlipidemia, diabetes mellitus, and coronary artery disease. However, this may be a risk inherent to this specific population and may not be applicable to the general population. Human studies in patients with anorexia nervosa and other eating disorders have shown the safety and tolerability of olanzapine. We will exclude anyone with a history of diabetes mellitus or hyperglycemia. We will also monitor the subjects closely during the study period and anyone who exhibits hyperglycemia (fasting glucose > 150 mg/dl or non-fasting glucose > 180 mg/dl), and/or rapid weight gain (> or = 5 kgs/week) will be taken off the study drug. Subjects will continue to be monitored for 14 days after completion of the study drug.

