4 ELIGIBILITY CRITERIA

Inclusion Criteria:

- Male or female between 18 and 80 years of age, inclusive.
- Has gastroparesis at screening (gastric half-time of emptying > upper limit of normal as determined by wireless motility capsule)
- Must have a > or = 6 month history of relevant symptoms of gastroparesis, (e.g., chronic post-prandial fullness, early satiety, postprandial nausea), patients will have a mean of the daily scores over a minimum of 7 days indicating > or = mild (2) assessed using the GCSI-DD during the screening period prior to randomization.
- A female subject is eligible to participate if she is of non-childbearing potential or child-bearing potential and agrees to use one of the approved contraception methods. Female patients must agree to use contraception for at least 5 days following the last dose of study medication.

- Male subject must agree to use of contraception. Contraception must be followed from the time of the first dose of study medication through at least 5 days after the last dose of study medication.
- BMI \geq 18 and < 30 kg/m2 (inclusive).
- Subjects on anti-hypertensive medications may be allowed to participate but should exercise caution given risk of orthostatic hypotension
- Subject has never had a gastrectomy, nor major gastric surgical procedure or any evidence of bowel obstruction or strictures within the previous 12 months
- Dosage of any concomitant medications has been stable for at least 3 weeks.
- Estimated (or measured) glomerular filtration rate \geq 30 mL/min.
- QTcB or QTcF < 450 msec or QTc < 480 msec in patients with Bundle Branch Block based on single or average QTc value of triplicate values obtained over a brief recording period.
- Capable of giving written informed consent, which includes compliance with the requirements and restrictions listed in the consent form.
- AST and ALT < 2xULN; alkaline phosphatase and bilirubin ≤ 1.5xULN; normal CBC, TSH, and prolactin levels.

Exclusion Criteria:

- Subject has a history of diabetes mellitus, hyperglycemia, hyperlipidemia, cardiovascular disease, cerebrovascular disease, seizures, hyperprolactinemia, Parkinson's disease, or dementia.
- Subject has a history of elevated glucose level (fasting blood glucose level of 100-126 mg/dl and/or non-fasting glucose level of 140-200 mg/dl)
- Subject has history of underlying schizophrenia, bipolar disorder, suicidal ideation/attempt, or has used olanzapine in the past.

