6 STUDY DESIGN AND PROCEDURES

This is a pilot study of 10 consecutive subjects ages 18 – 80 with documented delayed gastric emptying within the past 2 years and history of nausea, vomiting, bloating, anorexia, early satiation, post-prandial fullness, and weight loss for at least 6 months without structural or organic cause will be enrolled. This will be an open label trial without a placebo arm to determine efficacy and safety of the medication in this population. This will be a single center study with subjects being enrolled at the University of Michigan. [name] at Massachusetts General Hospital will act as a co-I and will assist with data analysis but will not enroll any patients. [name] will receive only de-identified information.

The study will consist of a screening/baseline period of up to 30 days, an 8-week treatment period, and a 14-day post treatment safety follow-up visit and assessment of symptoms.

Screening/Baseline:

Subjects will participate in a screening/baseline visit within 30 days prior to study dosing. Subjects will be instructed to fast prior to the screening visit at which time they will undergo blood sampling for complete blood count (CBC), complete metabolic panel (CMP), lipid profile, insulin, Hgb A1c, prolactin, TSH, and urine or blood pregnancy screen (if applicable). A baseline ECG will also be performed. Ghrelin levels will be measured. Baseline vital signs, height, weight, and BMI will also be calculated. They will also have their gastric emptying assessed by wireless motility capsule (WMC). To be eligible for the study, the subjects' gastric emptying time, as determined by WMC, needs to be greater than 5 hours. Potential subjects will complete the gastroparesis cardinal symptom index daily diary (GCSI-DD) evaluation, appetite visual analog score (VAS), and Bristol Stool Form Scale (BSFS) for a minimum of 7 days to determine baseline level of symptoms [41]. Questionnaires will be completed in the evening after dinner. Mean total GCSI-DD score must be ≥ 2 in order to qualify for the study.

Week 1 – Week 8:

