Subjects will initially start on olanzapine 2.5 mg by mouth daily to be taken at bedtime. Subjects will return on days 7 and 14 to determine response to medication. Medication dose can be increased to 5 mg on day 7 and 10 mg on day 14, respectively, based on incomplete symptom response, which is defined as a mean change in GCSI-DD score < 0.5 from baseline. Height and weight will be measured on Day 7. The total dose of olanzapine will not exceed 10 mg daily during this study. Subjects will be monitored for adverse events and undergo blood sampling for glucose, insulin, and Hgb A1c on day 14. Vital signs, height, weight, and BMI will also be evaluated. Subjects will be instructed to bring their study medication with them on day 14 for assessment of study drug accountability.

Subjects will be contacted by phone at least once within 2 weeks following the day 14 visit to assess for potential side effects. Subjects may also come in for an extra/optional study visit between the Day 14 and Day 35 visits, if warranted by side effects.

Subjects will return on day 35 to monitor for adverse events, vital signs, height, weight, BMI, and glucose check.

During the study, subjects will rate their gastroparesis symptoms on a daily basis by completing the GCSI-DD and appetite VAS questionnaires. Subjects will also record daily the number of stools and their consistency [42]. Subjects will be asked to complete all diaries after the evening meal. The subjects will fast prior to returning to clinic on the morning of day 56 to undergo assessment of their gastric emptying time by WMC and complete an appetite VAS. Blood sampling for LFTs, glucose, insulin, Hgb A1c, and ghrelin levels will be performed. Vital signs, height, weight, and BMI will also be measured. All remaining study medication will be returned to the clinical unit for final drug accountability. Subjects will continue to rate their gastroparesis symptoms for 14 days following the end of dosing.

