Adverse events, vital signs, and laboratory parameters will be assessed to monitor overall safety and tolerability of the medication. Common potential adverse effects of the medication include orthostatic hypotension, weight gain, hyperglycemia, hyperlipidemia, increased prolactin level, akathisia, somnolence, and tremor. Serious adverse effects include sudden cardiac death, diabetic coma, venous thromboembolism, cerebrovascular disease, seizure, and suicidal intent. A subject will be withdrawn from the study if they experience any serious adverse events or if they develop hyperglycemia (fasting glucose level > 150 mg/dl or non-fasting glucose level > 180 mg/dl), or weight gain (\geq 5 kg/wk). The FDA definition for serious adverse events (SAE) will be used which is defined as an AE resulting in any of the following outcomes: Death, a life-threatening adverse event, inpatient hospitalization or prolongation of existing hospitalization, a persistent or significant incapacity or substantial disruption of the ability to conduct normal life functions, or a congenital anomaly/birth defect related to the adverse event. Important medical events that may not result in death, be lifethreatening, or require hospitalization may be considered serious when, based upon appropriate medical judgment, they may jeopardize the patient or subject and may

require medical or surgical intervention to prevent one of the outcomes listed in this definition. The PI will determine whether the SAE is related or possibly related to the drug. The trial will stop if any SAE related to the drug is encountered. Subjects will be allowed to use ondansetron, promethazine, and/or prochlorperazine as rescue medications during the study. Laxatives, including Miralax, magnesium, Dulcolax, stool softeners, fiber supplements, and/or linaclotide may also be used during the study to treat underlying constipation. Subjects will not be allowed to use any prokinetic agents, such as Reglan, domperidone, or macrolide antibiotics (e.g. erythromycin) during the study. Rescue and concomitant medications (prescriptions or OTC medications) ongoing at the Screening Visit and/or started from the Screening Visit onwards until the last study related activity will be documented in the Prior and Concomitant Medication and Rescue medication pages of the Case Report Form (CRF). Subjects will be asked to monitor and record usage and frequency of rescue medications and laxatives used during the study.

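### The lipid profile is never scheduled on drug, although hyperlipidemia is a named risk and the fasting Day 56 draw could carry it

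*Combined protocol and SAP*

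**What the plan says.** Hyperlipidemia appears as a risk in several places. Section 1 (Background) includes it among the serious metabolic risks of second-generation antipsychotics. Section 3 (Expected Risks/Benefits, weight gain) says of weight gain on the drug: "This may also predispose the patient to develop underlying obesity, hyperlipidemia, diabetes mellitus, and coronary artery disease". Section 6 (Week 1 – Week 8) gives the common potential adverse effects as "orthostatic hypotension, weight gain, hyperglycemia, hyperlipidemia, increased prolactin level, akathisia, somnolence, and tremor". Section 4 excludes on history, in a criterion that begins "Subject has a history of diabetes mellitus, hyperglycemia, hyperlipidemia, cardiovascular disease", but sets no numerical lipid limit.

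Section 8 defines the primary outcome as both efficacy and safety. Section 6 says that laboratory parameters will be used to monitor safety and tolerability.

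The lipid profile is listed twice in Section 6: at the fasting screening visit, and at the Post-Treatment Assessment 14 days (plus up to 2) after the last dose. On Day 56, when the subject attends fasting and blood is taken, the list is: "Blood sampling for LFTs, glucose, insulin, Hgb A1c, and ghrelin levels will be performed". Lipids are not on it.

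**The concern.** The plan names a laboratory effect of the drug as common, makes safety part of its primary outcome, and then measures that effect only when the subject is not taking the drug. The other two metabolic effects in the same list, weight gain and hyperglycemia, are followed repeatedly during treatment. No reason is given for treating lipids differently, whereas Section 1 does explain why ghrelin is the only gut hormone measured.

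What is at stake is how a result of no lipid change would be read. A reader of the pilot could take it as reassurance about lipids on olanzapine, when it would describe subjects about two weeks after stopping. Section 1 says that the pilot may inform a larger placebo-controlled trial, so the misreading could carry forward.

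**Working it through.** No figure in the plan needs reproducing. The check sets the written schedule in Section 6 out visit by visit.

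| Visit | On drug? | Fasting stated? | Laboratory tests listed | Lipid profile |
|---|---|---|---|---|
| Screening | No | Yes | CBC, CMP, lipids, insulin, Hgb A1c, prolactin, TSH, ghrelin | Yes |
| Day 7 | Yes | No | None (height and weight only) | No |
| Day 14 | Yes | No | Glucose, insulin, Hgb A1c | No |
| Day 35 | Yes | No | Glucose | No |
| Day 56 | Yes | Yes | LFTs, glucose, insulin, Hgb A1c, ghrelin | No |
| Follow-up | No, 14 to 14 + 2 = 16 days after last dose | No | CBC, CMP, lipids, TSH, prolactin, insulin, Hgb A1c, ghrelin | Yes |

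Day 56 counts as on drug because dosing is at bedtime and the visit is in the morning, so the sample follows the previous evening's dose.

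**Count.** Lipid profiles per subject: 1 before treatment, 0 + 0 + 0 + 0 = 0 on treatment, 1 after treatment. The phone contact and the optional extra visit between Days 14 and 35 list no laboratory tests.

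**What the planned analysis can estimate.** Section 10 tests change from baseline by the post-treatment assessment with a paired test, and models change over all measurement times. For lipids there are two times, neither on drug. Let D be the mean change from screening to the end of treatment, r the fraction of D still present at follow-up, and f any shift caused by a difference in fasting state between the two samples. Then:

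observed change = r × D + f

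There is one observed quantity and three unknowns.

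- If r is about 1 and f = 0, the observed change equals D and nothing is lost.
- If r is below 1 and f = 0, the observed change is smaller than D.
- If r is near 0 and f = 0, the on-drug change would not be seen at all.

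The documents give no value for r. They do not say that the follow-up sample is fasting, so f = 0 cannot be assumed either. The multiple imputation in Section 8 does not help, because no subject has an on-drug lipid value from which to impute.

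**What a Day 56 sample adds.** Screening and Day 56 are both stated to be fasting, so their difference estimates D directly with f = 0. It is the only on-drug comparison in the schedule that is matched on fasting.

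**The case against.** The best defense is that the plan keeps its own promises. Aim 1 lists the safety laboratory tests and lipids are not among them. Lipids are not an efficacy endpoint, a titration input or a withdrawal trigger, and with 10 subjects any lipid estimate will be imprecise. If hyperlipidemia follows from weight gain, as Section 3 suggests, that pathway is observed on drug, because weight is recorded on Days 7, 14, 35 and 56. A weight-mediated lipid change might also persist for two weeks, in which case the follow-up sample would capture most of it.

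Most of this stands as a limit on severity. The omission changes no efficacy inference and contradicts no stated aim. It does not remove the gap: weight is not a lipid measurement, persistence for two weeks is as undocumented as reversal, and a small sample does not justify sampling at an uninformative time.

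Three stronger readings are tempting.

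- *The follow-up value is diluted by a known amount.* The documents give no reversal rate, so any percentage would rest on an assumed half-time. Slow or absent reversal is also possible.
- *The same fault applies to the ECG.* A reader might put the entry limit ("QTcB or QTcF < 450 msec or QTc < 480 msec in patients with Bundle Branch Block") and "A baseline ECG will also be performed" beside "Serious adverse effects include sudden cardiac death" and conclude that a later ECG is missing. No part of the documents links the drug to QTc change, and no aim or analysis claims anything about QTc. An entry screen alone does not imply repeat measurement.
- *Lipids are a laboratory threshold for entry.* Section 4 excludes on history of hyperlipidemia only, while it does set limits for liver tests, CBC, TSH and prolactin.

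**Conclusion.** The point holds for lipids, as a gap between the risks that the protocol names and the schedule that it writes. Followed exactly, the plan cannot observe the on-drug lipid change in any of its 10 subjects. Its only paired lipid comparison is screening against 14 to 16 days off drug, with fasting stated for the first sample and not for the second.

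That comparison would understate any effect that reverses on stopping. The degree is unknown, with retention anywhere up to about 100%. That dilution occurs is therefore a possibility, not a demonstrated bias. The absence of an on-drug value needs no assumption beyond reading the text as the full schedule. The Figure 1 timeline was not available for this check; if it shows a Day 56 lipid profile, the text and the figure need to be reconciled.

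It would be wrong to describe this as a breach of Aim 1. The weight is that of a cheap, worthwhile improvement to the safety half of the primary outcome.

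**What to change.** In Section 6 (Week 1 – Week 8), add the lipid profile to the Day 56 fasting draw. In Section 10, name screening to Day 56 as the lipid safety comparison. Report the follow-up lipid value separately as off-drug, and read the Day 56 to follow-up difference as reversal only if Section 6 (Post-Treatment Assessment) also requires that sample to be fasting. If Figure 1 lists laboratory tests by visit, update it to match.

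Cost: one assay for each of 10 subjects, 10 × 1 = 10 assays at most, on blood already being drawn at an existing visit, plus two or three sentences of protocol text. If the sponsor prefers not to add the assay, the report should say that lipids were measured only before treatment and about two weeks after it, and that the on-drug lipid effect was not assessed.

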Post-Treatment Assessment:

At the conclusion of 56 days of dosing, subjects will return for a follow-up visit 14 days (+ 2 days) after the last dose of study medication. All subjects will have blood sampling for CBC, CMP, lipid profile, TSH, prolactin, insulin, Hgb A1c, and ghrelin. Height, weight, and BMI will be calculated. One final appetite VAS will be completed. The duration of each patient's participation in the study from screening to follow-up visit will be approximately 14 weeks.

Subjects are free to discontinue participation in the study at any point. If a subject decides to prematurely discontinue from the study, they will be contacted within two weeks for safety follow-up visit(s). Reasons for withdrawal will be documented by the PI. If the reason for removal of a subject from the study is an AE, the principal specific event will be recorded on the CRF. The subject will be followed until the AE is resolved.

Gastric Motility:

Gastric motility will be tested by using the WMC wireless capsule system (The SmartPill Corporation, Buffalo, NY). This offers a potentially more complete examination into possible etiologies for gastroparesis including delayed gastric emptying as well as gastric and small bowel contractility abnormalities. We will follow the protocol for measuring gastric emptying by wireless motility capsule as described previously in the literature [43]. Gastric emptying time (GET) is defined as the duration of time from capsule ingestion to entry of the capsule into the duodenum. Subjects will swallow the WMC capsule with 50 ml of water followed by ingestion of a standardized meal comprising of a nutrient bar, which has a total caloric value of 255 kcal (72%)

carbohydrate, 24% protein, 2% fat, and 2% fiber) [44]. Because of the low risk of capsule retention especially once the capsule enters the colon, plain abdominal radiograph (KUB) will be performed only if there is no documentation of the capsule passing the ileocecal valve and the patient has symptoms of capsule retention. Pressure data recorded by the WMC capsule will be analyzed for 1 hour before and after the WMC empties the stomach (GET). The analyzed parameters are: number of contractions (Ct), and motility index defined as: MI = Ln (sum of pressure amplitudes * number of contractions +1) [45].

Stopping Criteria:

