10 STATISTICAL CONSIDERATIONS

Changes in measures from baseline will first be examined using descriptive statistics and graphical analysis. Significance of changes by the post treatment assessment will be determined using paired t tests or Wilcoxon rank sum tests, depending on the normality of the measures. Hierarchical regression will be used to analyze patterns of change across all measurement times, with time as a nested factor within subject. Adverse events will be summarized by proportions and 95% confidence intervals.

Sample size was based on variance estimates from prior studies using GCSI-DD and the appetite VAS in patients with gastroparesis [41, 47], and was computed using a 2-

sided type I error rate of 0.05. Conservatively using the largest variance reported for any of the GSCI subscales, and conservatively using a within-subject correlation of 0.6, a sample size of 10 patients will provide 88% power to detect a 1-point decrease in GCSI-DD, which we judged to be a clinically meaningful change in the subscales and total scale. For a more likely within-subject correlation of 0.8, power would be >99%. For the appetite VAS, we judged a 10 mm change to be clinically significant. Again conservatively using the largest of the reported variances, 10 patients will give 80% power to detect a 10mm change if the within-subject correlation is 0.6 and 97% power if the within-subject correlation is 0.8. A sample size of 10 subjects will also provide sufficient precision in parameter estimates from this study for use in power calculations for future studies of olanzapine in patients with gastroparesis.

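### Fasting is not specified for the Day 14, Day 35 and follow-up blood draws, so the planned change analyses can mix fasted and fed samples, and lipids have no assured fasted pair

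*Combined protocol and SAP*

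**What the plan says.** All the sampling rules are in Section 6.

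- **Screening:** "Subjects will be instructed to fast prior to the screening visit at which time they will undergo blood sampling". The panel includes the metabolic panel, lipids and insulin, and the same paragraph adds "Ghrelin levels will be measured".
- **Day 14:** subjects "undergo blood sampling for glucose, insulin, and Hgb A1c on day 14". Fasting is not mentioned.
- **Day 35:** "Subjects will return on day 35 to monitor for adverse events, vital signs, height, weight, BMI, and glucose check". Fasting is not mentioned.
- **Day 56:** "The subjects will fast prior to returning to clinic on the morning of day 56". Liver tests, glucose, insulin, Hgb A1c and ghrelin are drawn; lipids are not.
- **Follow-up, 14 days after the last dose, under the heading Post-Treatment Assessment:** "All subjects will have blood sampling for CBC, CMP, lipid profile, TSH, prolactin, insulin, Hgb A1c, and ghrelin". Fasting is not mentioned.

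Sections 3 and 6 set the glucose withdrawal limit at 150 mg/dl for a fasted value and 180 mg/dl for a non-fasted one.

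On analysis, Section 10 states: "Significance of changes by the post treatment assessment will be determined using paired t tests", with a rank-based alternative. It then adds a hierarchical regression over every measurement time. Neither analysis names fasting status, and no section says that it will be recorded.

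**The concern.** Glucose, insulin, lipids and ghrelin depend on recent food intake. The plan controls this at baseline and at the end of dosing, then stops controlling it at the visit whose name Section 10 uses for its change test. If some subjects come to follow-up after eating, the change from a fasted baseline contains a meal effect. With one arm of ten subjects, no control group carries the same meal effect, so nothing cancels it. If fasting status was not recorded, it cannot be adjusted for afterwards.

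What is at stake is mainly metabolic safety. Section 8 makes safety part of the primary outcome. Aim 1 relies on glucose and insulin both during the study and after treatment. Section 3 names hyperlipidemia as a risk of the drug, and Section 6 lists it among the common adverse effects.

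**Working it through.** The plan states no figure to reproduce. The check sets the fasting instructions beside the draws and then beside the analysis.

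**Step 1. Visits and draws (Section 6).** Glucose at screening and follow-up is taken to come from the metabolic panel.

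| Visit | Fasting instruction | Glucose | Insulin | Ghrelin | Lipids |
|---|---|---|---|---|---|
| Screening | yes | yes | yes | yes | yes |
| Day 14 | none | yes | yes | no | no |
| Day 35 | none | yes | no | no | no |
| Day 56 | yes | yes | yes | yes | no |
| Follow-up | none | yes | yes | yes | yes |

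**Step 2. Post-baseline measurements assured to match the fasted baseline.**

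- Glucose: 1 of 4 (Day 56)
- Insulin: 1 of 3 (Day 56)
- Ghrelin: 1 of 2 (Day 56)
- Lipids: 0 of 1
- Total: 1 + 1 + 1 + 0 = 3, out of 4 + 3 + 2 + 1 = 10

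**Step 3. Which pair is tested.** Section 10's phrase matches the heading of the follow-up visit. On that reading the tested pair is screening against follow-up: fasted against unspecified for all four analytes. If the phrase is instead taken to mean Day 56, the paired test is matched for glucose, insulin and ghrelin, but lipids have no Day 56 sample. The regression over all times still takes in the seven unspecified measurements (10 - 3 = 7).

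**Step 4. Form of the error.** Let f be the share of follow-up samples taken fed and m the mean meal effect in those subjects. Then

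observed mean change = true mean change + f × m.

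The second term is zero if everyone happens to fast (f = 0) and reaches m if nobody does (f = 1). With ten complete subjects, each fed sample moves the mean by one tenth of that subject's meal effect. The documents give neither f nor m for any analyte, so the term cannot be evaluated.

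**Step 5. What is unaffected.** Screening to Day 56 is fasted at both ends for glucose, insulin and ghrelin, and Day 56 is the end of dosing. Aim 3 asks whether the drug promotes ghrelin secretion, and this pair addresses that on treatment. Ghrelin and lipids are not drawn on Day 14 or Day 35, so for them the gap exists only at follow-up. Hgb A1c does not depend on fasting at the draw.

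**Step 6. Use of the Day 14 and Day 35 glucose values.** A reading above 150 and up to 180 mg/dl falls on different sides of the plan's two limits according to fasting state. That status therefore has to be known at each reading. This is a reason to record it and implies nothing about the limits themselves.

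**The case against.** The strongest reply is that the comparison that matters most is already sound. Day 56 is on drug and fasted, whereas follow-up is two weeks off drug. A reader might infer that the missing instruction confounds Aim 3 as a whole. The documents do not support that: only analyses that use follow-up ghrelin are exposed. This part of the reply stands.

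Second, the text is silent; it does not prescribe fed sampling. The subject timeline in Figure 1 is not shown and might carry a fasting mark. A reader might infer from the separate non-fasting glucose limit that the plan intends fed draws. That limit could equally serve unscheduled readings, such as the optional visit between Days 14 and 35. It shows that a non-fasted value was foreseen, not that fed samples are scheduled. This also stands, so the finding is that matching is not assured, not that it is known to fail.

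Third, it is tempting to size the bias from the gaps between the plan's limits: 180 - 150 = 30 mg/dl for withdrawal, or 140 - 100 = 40 mg/dl at the lower ends of the entry ranges. These are decision limits, not measured meal effects. The upper ends of the same entry ranges differ by 200 - 126 = 74 mg/dl, which shows how arbitrary the choice is. The subjects also have delayed gastric emptying. No figure in mg/dl is supported.

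Fourth, lipids are not among Aim 1's listed safety tests, and the sample size rests on symptom and appetite scores. Both are true and limit the weight of the point. But the lipid profile is drawn twice and hyperlipidemia is a named risk, so the one available lipid change will be read as safety evidence.

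Fifth, compulsory fasting on Days 14 and 35 would add burden where a non-fasting glucose limit already exists. This stands, and recording fasting status is enough at those visits.

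**Conclusion.** The concern holds in a limited form. On the visible text, seven of the ten scheduled post-baseline measurements of meal-dependent analytes have no stated fasting condition, and the only lipid change sets a fasted screening sample against an unspecified one. The paired test, read by its own wording, uses the follow-up visit, and the regression pools all times without a term for fasting status. The on-treatment ghrelin, insulin and glucose comparison is not undermined.

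The size in analyte units is unknown. It depends on how many subjects eat before the draw and by how much a meal moves each analyte, and the documents give neither.

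The conclusion rests on three assumptions: Figure 1 carries no fasting mark; the metabolic panel supplies glucose; and blood at screening and Day 56 is drawn before the 255 kcal capsule test meal, an order that Section 6 does not state. If the last is false at either visit, the matched pair is also in doubt.

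This is a cheap improvement worth making before enrolment, because fasting status that is not recorded cannot be recovered later.

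**What to change.** - In Section 6, extend the existing fasting instruction to the follow-up visit.
- Add a CRF field for fasting status, completed at every glucose, insulin, lipid and ghrelin draw, including Days 14 and 35.
- In Section 10, name screening to Day 56 as the main on-treatment comparison for glucose, insulin and ghrelin.
- For all other change analyses of these analytes, including the regression, match on fasting status or adjust for it.
- State that blood at screening and Day 56 is taken before the capsule test meal, if that is the intention.

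The cost is one more fasting visit per patient, one CRF field and a few lines of text. In a trial of ten, restricting to matched samples could lose some observations; adjustment avoids that loss at the price of estimating one more parameter.
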